**14.2.10. TTR assessed by central radiologist review**

Analysis of TTR based on central review will be analyzed in a similar way of TTR based on local review.

**14.2.11. Percentage change in tumor measurement from baseline**

The best percentage change in tumor measurement from baseline (according to local assessments) will be displayed using a waterfall plot for ES.

The best percentage change in tumor measurement from baseline in the subgroup of subjects in Japan will be examined separately at the time of the primary analysis (i.e. Stage 2 or at Stage 1 if study stops for futility).

#### **14.2.12. Duration of Follow-Up**

A summary of duration between first study treatment administration and cut-off date, and follow-up times for PFS/OS will be generated, which are defined as follows:

- Duration between first study treatment administration and cut-off date = (Cut-off date – Date of first study treatment administration + 1) / 30.4375 (months). This item will be summarized in months overall.
- Follow-up time = (Date of event or censoring – Date of first study treatment administration + 1) / 30.4375 (months) regardless of censoring. This item will be summarized in months overall.

The analysis will be performed for PFS based on local review and PFS assessed by central radiologist review. Date of censoring is the same as defined for main analysis of the PFS and OS.

Separate summaries will be generated for the subgroup of subjects in Japan.

In addition, a reverse Kaplan-Meier analysis will be performed for both PFS and OS to estimate the median duration of potential follow-up as described by Schemper and Smith (1996). Patients who were censored (e.g. lost to follow-up, withdrew consent, ongoing, etc) in the PFS (or OS) analysis will be considered as events for the purposes of estimating duration of potential follow-up. Patients who had a PFS (or OS) event for the purposes of the PFS (or OS) analysis will be censored at the date of the event. The same duration of time values used in the PFS (or OS) analysis will be used in this analysis. Kaplan-Meier estimated probabilities with corresponding 95% CIs (Kalbfleisch and Prentice 2002) will be presented at the same time points as in the PFS (or OS) analysis.

## 15. SAFETY ANALYSIS

All safety analyses will be presented on the FAS.

### 15.1. TREATMENT EXPOSURE

Duration of study drug exposure to any dose (in weeks), actual and relative dose intensity will be summarized.

The number of subjects with at least one dose reduction will be presented, along with reasons for the dose reduction. The same table will be provided for dose interruptions, and for dose reductions or interruptions. The number of subjects with at least one definitive dose reduction (i.e. subjects with a dose reduction and who did not re-escalate to the protocol-planned dose) will be described. The actual daily doses and reasons for dose reductions/interruptions will be listed in an individual basis for subjects with dose reductions/interruptions.

A dose interruption will be indicated in the eCRF by a dosing record with a total daily dose of 0 mg for one or more days.

To avoid over-counting interruptions, dosing records with 0 mg entered as last dosing record will not be counted as interruptions (those represent the reason for permanent discontinuation and will therefore be presented in the reason for treatment discontinuation analysis).

A dose reduction is defined as a decrease in dose from the protocol-planned dose and a decrease from the previous non-zero dose, even if this decrease has been directly preceded by an interruption. For example, for encorafenib, in the sequence of total daily dose 300 mg – 0 mg – 200 mg, the 200 mg dose will be counted as a reduction.

These analyses will apply for each study drug (encorafenib, binimetinib and cetuximab) individually on the FAS.

- **Duration of study drug exposure** (weeks)

This is the duration that the patient was exposed to the study drug and is defined as  $([\text{Date of last (non-zero) dose of study drug}] - [\text{date of first dose of study drug}] + [\text{days until next dose}]) / 7$ .

For encorafenib/binimetinib, [days until next dose] = 1.

For Cetuximab,

- before switch to a biweekly infusion: [days until next dose] = 7
- from switch to a biweekly infusion: [days until next dose] = 14

NB: In the initial version of the study protocol, patients were planned to switch to cetuximab infusions at dosage of 500 mg/m^2 administered every 2 weeks (i.e. D1 and D15) at C8D1, instead of weekly infusions at dosage of 250 mg/m^2 (except first administration with dosage of 400 mg/m^2). Following the COVID-19 pandemic outbreak, an Urgent Safety Measure (USM) was implemented to allow the investigators to perform Cetuximab infusions at dosage of 500 mg/m^2 administered every 2 weeks (i.e. D1 and D15) instead of weekly, whatever the cycle (even if the subject has not reached yet C8D1), after having evaluated the benefit/risk for the subject and in order to reduce the number of visit at hospital.

For subjects who benefited from this USM, records post-decision to switch to an administration every 2 weeks will be derived as follows:

- 1) First step: Among the subjects having received at least one dose of study treatment (complete or partial): only the subjects who didn't have their C8D1 before the 01MAR2020 and who didn't discontinue treatment before 01MAR2020 and who didn't discontinue cetuximab before 01MAR2020 are to be considered
- 2) Among the subjects selected from first step, subjects with an administrated dose > 400 mg/m^2 before C8D1 will be considered as having benefited from the USM.
- 3) This subset of subjects will be cross-checked with reason mentioned for dose modification.  
Dose modifications for reasons not related to COVID-19 pandemic will be excluded

The date of switch to a biweekly infusion for a given subject will be derived as the first date among selected records for this subject.

NB: any infusion after this date at dosage < 500 mg/m^2 will be considered as a dose reduction, even if occurring before C8D1.

Duration of study drug exposure will also be described as a discrete variable, with modalities t to < t+4 weeks (t being the duration of exposure, in weeks), such as: < 4 weeks / 4 - < 8 weeks / 8 - < 12 weeks / etc.

▪ **Relative dose intensity (RDI) (%)**

- **Cumulative actual dose (mg or mg/m^2)** is the total dose given during the study treatment exposure. The cumulative actual dose for a given patient is the sum of the actual dose received (mg or mg/m^2). The actual dose received for Cetuximab (mg/m^2) at cycle i is equal to the actual dose received (mg) at cycle i divided by the body surface area at the beginning of cycle i
  - NB: If needed, the BSA at a given timepoint will be derived according to formula displayed in section **Erreur ! Source du renvoi introuvable.** (with same rounding convention)

For encorafenib and binimetinib (daily dosing):

- Duration of planned exposure (this is not summarized in any exposure table) = [Date of EOT or data cut-off (the earliest one)] – [date of first dose of study drug] + 1
- Dose intensity (mg/day) = [Cumulative actual dose]/[duration of planned exposure]
- Cumulative planned dose (mg) = sum(protocol specified dose across each day of planned exposure)
- Planned dose intensity (mg/day) = [Cumulative planned dose]/[duration of planned exposure].  
For encorafenib, PDI = 300 mg/day. For binimetinib, PDI = 90 mg/day.
- Relative dose intensity (%) = 100 x [Dose intensity]/[Planned dose intensity]

For Cetuximab (intermittent dosing):

- Duration of planned exposure (this is not summarized in any exposure table) = [Date of EOT or data cut-off (the earliest one)] – [date of first dose of study drug] + 1
- Duration of planned exposure after switch to a biweekly infusion (this is not summarized in any exposure table) = [Date of EOT or data cut-off (the earliest one)] – [date of first dose of study drug] - [number of days with weekly infusion] + 1

- planned day of the first visit when switch occurred is the theoretical day (based on C1D1) of the first visit where the subject was under weekly regimen. It represents the duration subject was under weekly regimen.
  - For instance, for subjects who did not benefit from the USM and switched to biweekly infusions starting from C8D1, as initially planned in the protocol: planned day of the first visit when switch occurred = 197, meaning 196 (28\*7) planned days under weekly regimen.
  - For subjects who benefited from the USM, number of days with weekly infusion can be derived using the visit of switch to a biweekly infusion (as derived above) and the theoretical day of visits
- This is calculated only if date of EOT or data cut-off (the earliest one) is after the switch to a biweekly infusion (28 weeks in the initial protocol (i.e. Duration of planned exposure > 196 (28\*7) days) or USM)

Let xx be the planned day of the first visit under biweekly regimen (197 in the initial protocol, where dosed bi-weekly from week 29/C8D1 or planned day of the first visit when switch occurred for subjects with USM):

- o Number of planned doses = number of non-zero doses plus the number of interrupted doses.
  - if date of EOT or data cut-off (the earliest one) is within the first xx-1 days (i.e. Duration of planned exposure ≤ xx-1 days): Number of planned doses = floor([duration of planned exposure – 1]/[days between doses]) + 1  
with days between doses = 7 (dosed weekly for the first xx-1 days)
  - if date of EOT or data cut-off (the earliest one) is after xx-1 days (i.e. Duration of planned exposure > xx-1 days): Number of planned doses = (xx-1)/7 + floor([duration of planned exposure after xx-1 days – 1]/[days between doses]) + 1  
with days between doses=14 (dosed bi-weekly from day xx)

- Dose intensity (mg/m^2/dose) = [Cumulative actual dose]/[number of planned doses]
- Cumulative planned dose (mg/m^2) = sum(protocol specified dose across each planned day of dosing)
- Planned dose intensity(mg/m^2/dose) = [Cumulative planned dose]/[number of planned doses].

For Cetuximab, PDI (mg/m^2/week) = Cumulative planned dose (mg/m^2)/ duration of planned exposure (week), *taking into account the Cetuximab administration scheme (400 mg/m^2 intravenous (IV) at Cycle 1 day 1 then 250 mg/m^2 IV every week (QW) for the first xx days. Then, 500mg/m^2 IV every two weeks (Q2W)*

- Relative dose intensity (%)= 100\*[Dose intensity]/ [Planned dose intensity]

Separate summaries will be generated for the subgroup of subjects in Japan.

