## 9.5. CUT-OFF CONVENTIONS

All available data will be included at the time of the cut-off date.

Subjects continuing to receive study treatment at the time of analysis will have time-to-event data (e.g., PFS, DOR) censored at the time of last tumor assessment prior to the data cut-off point used, if the event has not been observed before. Ongoing events (e.g., AEs, concomitant medication, etc.) will be summarized for analysis using the data cut-off date as the date of completion, with an indication that the event is ongoing.

For subjects who drop out from the study with ongoing events, the discontinuation date will be used as the completion date of the event with the appropriate censoring.

Data obtained after the cut-off will not be displayed in any listings or used for summary statistics (e.g. laboratory values of samples taken after data cut-off, AE with onset date after data cut-off, etc.).

For exposure data, if the treatment was started before the cut-off date and ended after the cut-off date, the end date will be imputed by the cut-off date. This imputed date will be used for duration and cumulative dose derivations.

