#### **Adverse events leading to study treatment discontinuation or interruption**

The number and percentage of subjects with at least one AE leading to study treatment discontinuation will be presented by study drug, MedDRA System Organ Class (SOC) and Preferred Term (PT), overall and maximum Grade 3 or higher.

The same table will be provided for AEs having led to a study treatment interruption.

AEs having led to study treatment discontinuation will be listed, on an individual basis in the same way as serious adverse events previously described, during the study (from the date of the first study treatment administration onwards).

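### SAP 15.1 omits an interruption still open at the data cut-off, so a subject with no other interruption of that drug is missing from the interruption table

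*SAP*

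**What the plan says.** SAP 15.1 defines the event: "A dose interruption will be indicated in the eCRF by a dosing record with a total daily dose of 0 mg", lasting one or more days. It then makes an exception, intended to avoid over-counting: "dosing records with 0 mg entered as last dosing record will not be counted as interruptions". The reason given is that "those represent the reason for permanent discontinuation and will therefore be presented in the reason for treatment discontinuation analysis".

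The table counts subjects, drug by drug. For reductions, "The number of subjects with at least one dose reduction will be presented, along with reasons for the dose reduction"; then "The same table will be provided for dose interruptions".

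Three other provisions matter:

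- **SAP 9.5 (cut-off conventions):** "Data obtained after the cut-off will not be displayed in any listings or used for summary statistics". Exposure that runs past the cut-off is closed on the cut-off date.
- **SAP 12 (disposition):** the discontinuation table covers only subjects who have discontinued study treatment, by reason.
- **SAP 15.2:** interruptions recorded as the action taken on the adverse event page are tabulated separately: "The same table will be provided for AEs having led to a study treatment interruption".

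Protocol 13.9.1 asks for the number of subjects with dose changes or interruptions and does not exclude a final 0 mg record.

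**The concern.** The exception is unconditional, but its justification covers only subjects who have permanently stopped the drug. SAP 6.6 plans three analyses (stage 1, stage 2 and end of study), and SAP 9.5 itself provides for "Subjects continuing to receive study treatment at the time of analysis". The protocol adds an extension period from 28 December 2020 for subjects still benefiting. Some subjects may therefore be on treatment at any of these cut-offs.

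Temporary holds are not momentary. Protocol Table 14 works with limits of 14 or 21 days for several toxicities, and Protocol 5.7.1 sets its discontinuation criterion at more than 28 consecutive days. A hold that happens to be open on the cut-off date is an ordinary event.

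At stake is the number of subjects with at least one interruption, with reasons, which is a standard tolerability summary. Any error from this source runs one way, towards fewer interruptions. If the individual listing in 15.1 uses the same definition, a subject with no other reduction or interruption drops out of that as well.

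**Working it through.** The plan states no figure for this point, so there is nothing to reproduce. The check applies the written rules in order and then sizes the effect.

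**Step 1. The rules in sequence.** Take a subject whose drug is held before the cut-off and restarted after it.

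1. The restart record falls after the cut-off, so SAP 9.5 removes it.
2. The 0 mg record is closed at the cut-off and becomes the last dosing record.
3. SAP 15.1 therefore does not count it.
4. The subject has no end-of-treatment page. SAP 9.1.2 treats a subject with no end date and no such page as ongoing, and SAP 12 has no discontinuation to report.

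If this was the only interruption of that drug, the subject is in neither table.

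**Step 2. Six dosing histories for one drug.** The SAP rule drops the last record if it is 0 mg, then counts the subject if any other 0 mg record remains. The proposed rule drops the last 0 mg record only if the drug has been permanently discontinued and the record's reason is the discontinuation reason.

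| History | Counted under SAP 15.1 | Counted under proposed rule | Discontinuation table |
|---|---|---|---|
| A. On treatment, only interruption open at cut-off | No | Yes | Absent |
| B. On treatment, an earlier resolved interruption and one open at cut-off | Yes | Yes | Absent |
| C. Held for toxicity, then stopped for progression, a single 0 mg record with the toxicity reason | No | Yes | Progression |
| D. As C, with a second 0 mg record for the discontinuation | Yes | Yes | Progression |
| E. Discontinued for an adverse event | No | No | Adverse event |
| F. Resolved interruption | Yes | Yes | Absent |

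History A is the defect. History E shows that the proposed rule keeps the SAP's protection against over-counting.

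**Step 3. Size of history A.** None of the inputs below is in the documents, apart from 90 as the target number of treated subjects with a centrally confirmed mutation. The full analysis set could be larger.

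Subjects lost per drug = N × a × b × c, where

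- N = 90;
- a = share still on the drug at cut-off, assumed 10% to 50%;
- b = share of those in an open interruption, assumed 5% to 20%;
- c = share of those with no earlier interruption of that drug, assumed 30% to 60%.

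Low end: 90 × 0.10 × 0.05 × 0.30 = 0.135, about 0.1 subject (0.135/90 = 0.15%).

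High end: 90 × 0.50 × 0.20 × 0.60 = 5.4 subjects (5.4/90 = 6.0%).

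With a = 25% and b = 10%, the result is 90 × 0.25 × 0.10 × c, that is 0.7 (c = 30%) to 1.35 (c = 60%).

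**The case against.** Four points limit how far this goes, and all of them stand.

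- **Most subjects with a final 0 mg record do not disappear.** A reader might infer that everyone in a hold at cut-off is lost. The table counts subjects with at least one interruption, so a subject with an earlier interruption of the same drug stays in it (history B). Only the last episode and its reason are lost.
- **Toxicity followed by progression.** A reader might infer that a hold for toxicity vanishes whenever treatment is later stopped for progression. That depends on how sites enter the records. With one continuous 0 mg record the hold is lost (history C). If the discontinuation has its own closing record, as the SAP's rationale suggests, the hold is counted (history D). The documents do not show the entry convention, so this case is not established.
- **The toxicity information is not lost.** Interruptions recorded as the action taken for an adverse event are tabulated by drug in SAP 15.2, including for events of special interest. For encorafenib and binimetinib, planned exposure in 15.1 runs to end of treatment or cut-off, so relative dose intensity still reflects the gap. Interruptions for other reasons have no counterpart in 15.2.
- **Disagreement between 15.1 and 15.2 would not by itself show an error.** One counts any 0 mg record and the other counts only actions on the adverse event page. They need not match, whatever is done with the last record.

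It can also be argued that SAP 9.5 already has ongoing events shown as ongoing. That sentence gives adverse events and concomitant medication as its examples and does not name dosing records. It therefore does not override the explicit exclusion in 15.1.

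**Conclusion.** The point holds for an interruption open at the data cut-off in a subject who has not permanently discontinued that drug. There the stated premise is false, the written rule gives too low a count, and no other SAP text corrects it. The subject is missing from the interruption table only if that hold is the sole interruption of the drug.

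The documents do not allow the effect to be sized. Roughly 0 to 5 subjects per drug follows from the assumed shares above and would change with them; a firmer statement that several subjects per drug are lost is not supported. The table is descriptive, SAP 8 treats everything except the primary test as exploratory, and confirmed response rate is untouched. This is a small correction worth making because the bias has a known direction and is cheap to remove.

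**What to change.** Replace the exclusion in SAP 15.1 with:

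> A last record of 0 mg is excluded from interruptions only if that study drug has been permanently discontinued by the cut-off and the record's reason is the reason for discontinuation; otherwise it is counted as an interruption with its recorded reason, flagged as ongoing at cut-off where applicable.

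The cost is one SAP sentence and a small programming change. The rule needs a discontinuation status and reason for each drug. SAP 15.2 describes a drug-specific withdrawal action on the adverse event page, and SAP 11.2.4 refers to an end-of-treatment form. Whether the dosing pages hold the same information for other reasons should be confirmed before programming.

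Tying the exclusion to a record that starts on the date of the discontinuation decision may look simpler, but it would not work. Protocol Table 14 often has dosing interrupted first and permanently stopped later if the event does not resolve. The 0 mg record would then start before the decision, and one episode would count as both interruption and discontinuation. The only decision date that the SAP defines (11.2.4) comes from the end-of-treatment form and is not given by drug.

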Methodology:	
This is a multinational, multicenter, open-label, single-arm phase II study to evaluate the combination of encorafenib, binimetinib and cetuximab in subjects with BRAF^{V600E} mutant mCRC who have not received any prior systemic therapy for metastatic disease.
 
Subjects will be eligible for the study based on identification of a BRAF^{V600E} mutation in the tumor tissue as determined by local laboratory result obtained at any time prior to Screening. Only polymerase chain reaction (PCR) and next generation sequencing (NGS)-based results will be acceptable. The BRAF mutation status must be confirmed by central laboratory no later than 30 days after the first dose of study treatment. In cases where there is discordance between the local assay and central laboratory results, or if the central laboratory is not able to confirm presence of a BRAF^{V600E} mutation due to inadequate or poor sample condition or insufficient amount of tumor cells in sample within 30 days of initiating study therapy, subjects may only continue treatment if there is no clinical indication of deterioration or disease progression and the Investigator determines that the subject is deriving benefit. In such instances, subjects must be informed that the BRAF mutation status is unconfirmed and must sign a separate informed consent form (ICF) that includes this information and describes alternative treatment options.
 
Main study period design (treatment phase) The Main study period will include two stages according to a two-stage design.
 
Stage 1: In the first stage, 40 subjects will be treated. In case of discordance in the results between the local assay and the central laboratory (potential false-positive local result), or lack of BRAF^{V600E} confirmation, subject will be replaced for the primary analysis of the futility analysis. If there are 11 or fewer confirmed responses (CR or PR) in the 40 treated subjects with a centrally confirmed BRAF^{V600E} mutation, the study will be stopped. Otherwise, additional subjects will enter stage 2. Stage 2 may be initiated as soon as 40 subjects with a centrally confirmed BRAF^{V600E} mutation are treated and confirmed responses are observed in at least 12 subjects.
 
Stage 2: 50 additional subjects will be treated, for a total of 90 subjects with a centrally confirmed BRAF^{V600E} mutation. In case of discordance in the results between the local assay and the central laboratory (potential false-positive local result), or lack of BRAF^{V600E} confirmation, subjects enrolled in the stage two of the trial will be replaced for the primary analysis.
 
If at any time during the study, either in stage 1 or in stage 2, there is discordance between the local assay and the central laboratory in 3 subjects ($\geq 3\%$ of the total targeted 90 treated subjects) or impossibility to confirm the BRAF^{V600E} mutation in 6 subjects ($\geq 6\%$ of the total targeted 90 treated subjects), all subsequent subjects will be required to have BRAF^{V600E} determined by the central laboratory prior to study treatment assignment. For the statistical design, please refer to the statistical section hereunder.
 
Treatment will be administered in 28-day cycles until disease progression, unacceptable toxicity, withdrawal of consent, initiation of subsequent anticancer therapy or death.
 
An independent Data Safety Monitoring Committee (iDSMC) will review the available safety information at regular intervals as defined in the iDSMC charter.
 
Main study period will end, as initially planned, 1 year after the start of study treatment of the last subject enrolled (as the last enrolled subject started study treatment on 27 Dec 2019, Main study period will end on 27 Dec 2020).

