Since implementation of the Urgent Safety Measure on 26 Mar 2020, in order to ensure the subjects' safety in the clinical trial by decreasing the number of clinic visits in the context of COVID-19 pandemic, Cetuximab infusions can be given every two weeks at the dose of 500 mg/m² administered as a 120-min IV infusion (i.e. on D1 and D15 of each cycle) regardless of the cycle number, after the investigator has evaluated the benefit/risk ratio for the subject with regards to Covid-19 pandemic.

If there was a dose modification prior to switching to the biweekly schedule, the total dose per cycle should be maintained (i.e. 200mg/m² QW, may be changed to a 400mg/m² Q2W).

From 28 Dec 2020, access to study treatment will be provided through a Study extension to all subjects whom the investigator considers are continuing to benefit from study treatment (i.e. do not experience unacceptable toxicities and none of the treatment discontinuation criteria are met) until:

- the last ongoing subject will discontinue study treatments (including 30-day Safety Follow-Up visit) for any reason (unacceptable toxicity, progression of disease, subject's decision, withdrawal of consent, initiation of subsequent anticancer therapy or death),
- or binimetinib/encorafenib are commercially available in the first line setting of *BRAF*^{V600E} mutated mCRC,

- or the binimetinib/encorafenib development program is stopped, whichever comes first.

The same study treatment doses and schedule as for Main study period will be applicable for the Study extension period (including dose modification recommendations).

After discontinuation of study treatment (during Main study or Study extension periods), there will be a 30-day safety follow-up period. Subjects will then enter a survival follow-up period until the End of the Study.

BRAF TESTING:

Because time to treatment initiation is critical for untreated *BRAF*^{V600E} mCRC subjects, will be eligible for the study based on identification of a tumoral *BRAF*^{V600E} mutation as determined by local laboratory result obtained at any time prior to Screening. Only polymerase chain reaction (PCR) and next generation sequencing (NGS)-based local assays results will be acceptable.

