## 5. LIST OF ABBREVIATIONS AND DEFINITION OF TERMS

AE	Adverse Event
AESI	Adverse Event of Special Interest
ALT	Alanine aminotransferase
AST	Aspartate aminotransferase
ATC	Anatomical Therapeutic Chemical classification
BID	Bis in Die
BMI	Body Mass Index
BOR	Best Overall Response
BOCR	Best Overall Confirmed Response
BP	Blood Pressure
BSA	Body Surface Area
CK	Creatine Kinase
CI	Confidence Interval
COVID-19	Coronavirus Disease 2019
CR	Complete Response
CtDNA	Circulating tumor DNA
CT scan	Computed Tomography scan
DBP	Diastolic Blood Pressure
DI	Dose Intensity
eCRF	Electronic case report form
ECG	Electrocardiogram
EQ VAS	EuroQol Visual Analog Scale
ES	Efficacy Set
FA	Fluorescein Angiography
FAS	Full Analysis Set
FPFV	First Patient First Visit
HR	Heart Rate
ICH	International conference on harmonisation of technical requirements for registration of pharmaceuticals for human use
KM	Kaplan-Meier
LLT	Lowest Level Term
LPLV	Last Patient Last Visit
LVEF	Left Ventricular Ejection Fraction
MedDRA	Medical Dictionary for Regulatory Activities
MSI	MicroSatellite Instability
NGS	Next Generation Sequencing
OCT	Optical Coherence Tomography
ORR	Overall/Objective Response Rate
PD	Progressive Disease
PDI	Planned Dose Intensity
PFS	Progression-Free Survival
PGIC	Patient Global Impression Change

PK	Pharmacokinetic
PP	Per Protocol Set
PCR	Polymerase Chain Reaction
PR	Partial Response
PT	Preferred Term
QD	Quaque Die (once daily)
QoL	Quality of Life
QTcF	QT interval corrected for heart rate using Fridericia's formula
QW	Quaque Week (once a week)
Q2W	Quaque 2 Weeks (once every 2 weeks)
RBC	Red blood cells
RDI	Relative Dose Intensity
RECIST	Response Evaluation Criteria In Solid Tumours
SAE	Serious Adverse Event
SAP	Statistical Analysis Plan
SBP	Systolic Blood Pressure
SC	Steering Committee
SD	Stable Disease
StD	Standard Deviation
SEM	Standard Error of Mean
SOC	System Organ Class
SPC	Summary Of Product Characteristics
TA	Tumor Assessment
TEAE	Treatment Emergent Adverse Event
TESAE	Treatment Emergent Serious Adverse Event
ULN	Upper Limit Normal
USM	Urgent Safety Measure
VAS	Visual Analysis Scale
WBC	White Blood Cells
WHODrug	World Health Organisation Drug

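### SAP 15.1 defines cetuximab planned dose intensity on two bases, per planned dose and per week, and only the per-dose one matches the dose intensity it is divided into

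*SAP*

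**What the plan says.** SAP section 15.1, under cetuximab (intermittent dosing), gives four lines that bear on RDI.

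- Dose intensity: "Dose intensity (mg/m 2 /dose) = [Cumulative actual dose]/[number of planned doses".
- Planned dose intensity, in a bullet: "Planned dose intensity(mg/m 2 /dose) = [Cumulative planned dose]/[number of planned doses".
- Directly below that, a line specific to cetuximab: "For Cetuximab, PDI (mg/m 2 /week) = Cumulative planned dose (mg/m 2 )/ duration of planned exposure (week". It goes on to refer to the dosing scheme, including the switch to two-weekly infusions.
- RDI: 100 times "Dose intensity]/ [Planned dose intensity".

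The SAP abbreviation list (section 5) expands PDI as "Planned Dose Intensity", so the second and third lines name the same quantity. No per-week dose intensity is defined for cetuximab.

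The two oral drugs are on one basis throughout, mg/day, and the drug-specific line under the same bullet gives the value in that unit: "For encorafenib, PDI = 300 mg/day. For binimetinib, PDI = 90 mg/day".

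Protocol section 13.9.1 and SAP section 15.1 both commit to summarising RDI for each study drug. SAP section 15.1 repeats the exposure summaries for subjects in Japan.

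**The concern.** A ratio of dose intensities is meaningful only if both parts share a basis. The per-dose planned value matches the per-dose dose intensity; the per-week value has no counterpart to divide into it. The two agree only when the number of weeks equals the number of planned doses, as after whole weeks of weekly dosing. Once infusions move to every two weeks they separate.

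A programmer who treats the cetuximab-specific line as the value to use, as the corresponding encorafenib and binimetinib line can be used, would put a weekly denominator under a per-dose numerator. The resulting RDI would depend on the day of the schedule switch and on time on treatment. Subjects who switched early under the Urgent Safety Measure (USM) would not be comparable with those who switched at week 29, and a sustained dose reduction could be invisible in the RDI column.

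**Working it through.** **Plan's own figures.** The documents print no cetuximab PDI or RDI, so there is none to reproduce. The neighbouring values do reproduce: 28 × 7 = 196 planned days of weekly dosing; encorafenib 4 × 75 = 300 mg/day; binimetinib 2 × 45 = 90 mg/day.

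**Inputs.**
- Planned doses (SAP 15.1), with duration D in days and xx the planned day of the first two-weekly visit: floor((D − 1)/7) + 1 up to day xx − 1; afterwards (xx − 1)/7 + floor((D − (xx − 1) − 1)/14) + 1.
- Planned amounts (SAP 6.1): 400 mg/m² once, then 250 weekly, then 500 every two weeks.
- xx = 197 for the switch at Cycle 8 Day 1 (SAP 15.1).
- xx = 99 for a USM switch. The protocol synopsis states "as the last enrolled subject started study treatment on 27 Dec 2019", and Protocol 4.1 has "Since implementation of the Urgent Safety Measure on 26 Mar 2020". Counting 27 Dec 2019 as day 1, 26 Mar 2020 is day 91. The next Day 1 or Day 15 visit is Cycle 4 Day 15, planned day 99. Subjects who started earlier were at day 91 or later on that date.
- Day 240 is 7.9 × 30.4375, from the median time on the triplet in Protocol 1.3. Those patients were previously treated and some were still on treatment, so it is only indicative.

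**Matched basis.** RDI = 100 × (actual/doses) ÷ (planned/doses) = 100 × actual/planned. Full compliance gives 100% at every duration.

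**Mixed basis.** RDI = 100 × (actual/doses) ÷ (planned/weeks). With full compliance this is 100 × weeks/planned doses.

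| Switch day | Day | Weeks | Planned doses | Cumulative planned (mg/m²) | PDI per dose | PDI per week | Mixed RDI, full compliance |
|---|---|---|---|---|---|---|---|
| 197 | 196 | 28 | 28 | 7,150 | 255.36 | 255.36 | 100.0% |
| 197 | 197 | 28.14 | 29 | 7,650 | 263.79 | 271.83 | 97.0% |
| 197 | 203 | 29 | 29 | 7,650 | 263.79 | 263.79 | 100.0% |
| 197 | 240 | 34.29 | 32 | 9,150 | 285.94 | 266.88 | 107.1% |
| 197 | 364 | 52 | 40 | 13,150 | 328.75 | 252.88 | 130.0% |
| 197 | 365 | 52.14 | 41 | 13,650 | 332.93 | 261.78 | 127.2% |
| 99 | 112 | 16 | 15 | 4,150 | 276.67 | 259.38 | 106.7% |
| 99 | 196 | 28 | 21 | 7,150 | 340.48 | 255.36 | 133.3% |
| 99 | 364 | 52 | 33 | 13,150 | 398.48 | 252.88 | 157.6% |
| 99 | 365 | 52.14 | 34 | 13,650 | 401.47 | 261.78 | 153.4% |

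During weekly dosing the mixed figure is at or below 100%. At day 10, for example, there are 2 doses and 650 mg/m², so 325 ÷ 455 = 71.4%. After the switch it drops at each planned dose, climbs between doses and trends upward.

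**Reduced dosing.** Take a subject at dose level -1 of Protocol Table 8 (200 weekly, 400 two-weekly) for every dose after the first, with the switch at day 197.
- Day 240: actual = 400 + 27 × 200 + 4 × 400 = 7,400. Correct RDI = 7,400/9,150 = 80.9%. Mixed RDI = (7,400/32)/266.88 = 86.7%.
- Day 364: actual = 400 + 27 × 200 + 12 × 400 = 10,600. Correct RDI = 10,600/13,150 = 80.6%. Mixed RDI = (10,600/40)/252.88 = 104.8%.

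**The case against.** The strongest reply is that the text already points to the right basis. The RDI formula uses the full names of the two bulleted items, both printed per dose and both divided by the number of planned doses. The per-week line prints a visibly different unit and has no partner. The 300 and 90 mg/day values for the oral drugs are simply what their own bullet's formula yields, so they set no precedent for a drug-specific line overriding a bullet. The weekly value may also have been meant as a schedule-neutral description: with the switch at week 29 it moves only from 255.36 at 28 weeks to 252.88 at 52 weeks, while the per-dose value rises from 255.36 to 328.75.

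Much of this stands. The per-dose reading is the likelier one and gives a correct RDI. It does not settle the matter, because the SAP gives one quantity two formulas and nowhere says that the weekly one is for description only or stays out of RDI.

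Two further points qualify the illustrations but not the conflict. SAP 15.1 screens for USM subjects from 01 March 2020 rather than 26 March, so a subject could be derived as switching before day 99; fewer planned doses would then make the mixed figure larger. And planned exposure runs to the end-of-treatment date. Protocol 9.1.9 allows that visit up to 14 days after the last dose, so if the visit date is used, planned doses may be counted after treatment has stopped and even the per-dose RDI may fall below 100%.

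**Conclusion.** The concern holds as a minor one. The duplicate definition is plain in the text and needs no assumption. Its numerical effect is conditional on the per-week line being programmed into RDI. In that case, with the switch at week 29 and full compliance, RDI is overstated by 7.1 percentage points at day 240 and by 30.0 at day 364; a USM switch at day 99 overstates it by 57.6 points at day 364. These figures assume doses on the planned days and planned exposure ending at the stated day.

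The reach is limited to the descriptive cetuximab RDI summary, overall and for Japan. Duration of exposure, dose reductions and interruptions are reported separately in SAP 15.1, and SAP section 8 treats everything except the primary endpoint test as exploratory. No endpoint, analysis set or decision rule is affected.

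**What to change.** Choose one basis and say so. Either delete the per-week line and keep planned dose intensity per planned dose, or define both dose intensity and planned dose intensity per week of planned exposure. Either way RDI reduces to 100 × cumulative actual dose / cumulative planned dose. If a weekly planned intensity is wanted as a description, give it a different name and state that it does not enter RDI.

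Then run the exposure program on a fully compliant 52-week test subject, with the end of planned exposure set so that no planned dose falls after the last dose given. The result must be 100%. The cost is a one-line SAP correction and a program check; no new data are needed.
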